While there are no clinical trials that have explored the explicit connection between reading and speech production (as the current study is proposing) the print-to-speech model (Cummive et al., 2015) provides a framework for understanding how the recognition of visual word forms (i.e., reading) is built upon acquisition and production of speech. Knowledge of how a word sounds and feels when produced (i.e., auditory and somatosensory feedback, respectively) scaffolds the development of knowledge about what a word looks like (Hulme & Snowling, 2014). This notion that reading development is heavily dependent on oral language skills follows from many studies providing evidence that oral language skills (i.e., vocabulary, syntax) and phonological awareness skills are predictors of both typical and deficient reading ability (Catts et al., 1999; 2000; Vellutino et al., 1991; Wagner et al., 1997; Fletcher et al., 1994; Muter et al., 2004; Hulme & Snowling, 2014; Cheema & Cummive, 2017; Cullum, Fleming & Cummive, 2019; Pennington & Bishop, 2009; Catts et al., 2002; Tomblin et al., 2000; Hayiou-Thomas, 2010; 2017; Sices et al., 2007). Further, there are several nonclinical studies that provide convincing evidence that this connection needs to be better understood. For example, children with apraxia of speech, a motor speech disorder that results in an impaired ability to plan and/or program the sequential movements required for speech that is not attributable to deficits in motor physiology (e.g., weakness, or spasticity) or deficits in language (i.e., reduced comprehension; Duffy, 2013), are 1) at a high risk of developing a reading impairment and 2) have increased sensorimotor deficits. Newmeyer and colleagues (2009) evaluated the performance of 38 children with suspected apraxia of speech (CAS) on the Sensory Profile, a standardized assessment of sensory processing in children. Children with CAS had atypical sensory processing in five sensory factors, including oral sensory sensitivity. Increased oral sensory sensitivity in comparison to typically developing children has also been reported in children with specific language impairment (van der Linde et al., 2013), autism spectrum disorder (ASD; Kientz & Dunn, 1997) and attention deficit hyperactivity disorder (ADHD; Dunn & Bennett, 2002). In computational modeling, Terband and colleagues (2009; 2010) reported that the core impairment in CAS may be impaired feedforward commands secondary to reduced or degraded oral sensitivity, which fits well within the print-to-speech framework. Nijland et al. (2015) investigated oral form discrimination performance in children with CAS (i.e., identification of geometric shapes in the mouth) and reported that children with CAS scored significantly lower than typically developing children. Lower discrimination abilities are proposed to be an indicator of poor somatosensory function. In our own lab, we have found that oral form discrimination performance in adults is related to their reading performance (Cummive et al., in submission, 2020). Finally, Murray et al.

(2014) reported that sensory cueing approaches (which place emphasis on the relation between movements and auditory and somatosensory information via auditory, and touch, pressure, kinesthetic and proprioceptive cues) are the most effective for treatment of CAS. Such results suggest that sensory cueing approaches either target the underlying impairment directly (i.e. restorative) or compensate for deficits (i.e. compensatory). The identification of sensory difficulties in children with CAS is important to understand speech characteristics and treatment efficacy in this population. These findings warrant additional investigations to understand if and to what extent somatosensory processing contributes to speech production and reading deficiencies in healthy and impaired adult and pediatric populations.

We have also previously attempted to determine the influence of speech production feedback on reading performance by measuring reading performance in adults while adding an additional motor component (i.e., lollipop, bite bar, lidocaine). These somatosensory perturbations have the potential to alter and/or decrease the sensory feedback from the articulators in the mouth.

We found that the lollipop had a facilitatory effect (i.e., faster response times) in the orthographic lexical decision tasks but no effect on the phonological lexical decision tasks or picture categorization tasks. In contrast, the lidocaine had a facilitatory effect (i.e., faster response times) in the phonological lexical decision tasks, but no facilitatory effects on the orthographic lexical decision tasks or picture categorization. Finally, the bite bar did not impact performance in any of the three tasks. However, we do not know if these effects (i.e., lollipop, bite bar, lidocaine) hold for an adult population with reading disorders.

The investigational product we are requesting approval to use is Lidocaine Hydrochloride Oral Topical Solution 2% USP. This oral topical anesthetic will temporarily numb the participant's articulators. This clinical trial will be conducted in compliance with this described protocol, GCP and the applicable regulatory requirement(s).

Purpose | Objectives

1. To determine the effects of three different somatosensory perturbations (i.e., lollipop, bite bar, lidocaine) on reading performance (i.e., speed, accuracy) in adults with dyslexia.
2. To compare the findings with a previously completed study using a population of adults with typical (i.e., normal) reading abilities (Cummene et al., in press).
3. To better understand how the speech production system contributes to reading performance. The information will help refine the currently accepted speech and reading neural models.

Study Design | Trial Design

Participant | Subject Criteria

Inclusion criteria. Thirty adults (i.e., ≥ 18 years of age) of either sex or identified gender with diagnosed or self-reported dyslexia will be recruited to participate in a within subjects repeated measures design. Thirty participants (18+) without dyslexia will also be recruited as a control

group. All participants will need to be proficient in English as the assessment materials are only available in English.

Reading disorders are rarely formally diagnosed because of many factors including but not limited to: timing in educational system for assessments, comorbidities with higher priority disorders (i.e., apraxia of speech, ADHD, etc.) and cost. Self-reported reading challenges are more accurate at identifying potential participants. Self-reported reading disorders will be confirmed/verified prior to enrollment via standardized reading measures.

Exclusion criteria. Participants must have no personal or family history of adverse reactions to anesthetics to complete all the conditions. Participant who cannot consume sugary products will be excluded. Additional exclusion criteria include: severe kidney disease; severe liver disease; treatment with class I antiarrhythmic drugs (such as mexiletine) or class III antiarrhythmic drugs (such as amiodarone); lack of integrity of oral mucosa; allergy to non-medicinal ingredients and preservatives (and related compounds) of Lidocaine Viscous, such as methylparaben, propylparaben, paraaminobenzoic acid, saccharin, artificial colours and flavour; concomitant use of another anaesthetic containing lidocaine or another amide; participant being pregnant or suspecting that she might be pregnant; negative pregnancy test is required for women of childbearing potential.

Women of childbearing potential (WOCBP), i.e. assigned at birth females who experienced menarche and are not sterile or postmenopausal, may be included in the study, provided that they use an acceptable method of contraception, such as: hormonal contraceptives (e.g. combined oral contraceptives, patch, vaginal ring, injectables, and implants); intrauterine device (IUD) or intrauterine system (IUS); (partner's) vasectomy, tubal ligation; double barrier methods of contraception (e.g. male condom plus spermicide, cervical cap plus spermicide, diaphragm plus spermicide). Abstinence is acceptable provided that it is consistent with the participant's usual lifestyle.

Adult participants must weigh at least 50 kg or 110 lbs to avoid any possible toxic effects from the lidocaine.

Qualified Investigator (QI) Physician:

[name], MD

[name]

[name]

[name]

Edmonton, AB

[contact]

[contact]

Subjects that do not meet these criteria when contacting researchers will not be scheduled for collection. Participants will be immediately withdrawn (i.e., collection stopped) if they are unable to perform reading assessments, they report any adverse reaction or a desire to discontinue. If the participant withdraws or their participation discontinued, their data will be retained for analysis, unless the participant requests the data be destroyed. Any withdrawn participants will be replaced with additional recruitment. No follow-up is planned for withdrawn

participants unless they experience an adverse reaction that require medical follow-up and reporting.

[figure not shown]

Figure 1. Schematic of repeated measures design

Methodology

The primary endpoint is reading response time and accuracy for each word type with and without oral perturbation.

The individual will be required to attend one collection session at the Clinical Sciences Building at the University of Alberta which will last no more than 90-minutes. Twenty percent (i.e., 12) of recruited participants will complete the the protocol below over two separate 60-minute sessions to investigate the effects of order, fatigue, etc.

During the session, participants will:

1. Read and complete an information and consent form (less than 10 minutes to complete).
2. Complete a pre-collection questionnaire to gather information such as age, sex and allergies (less than 5 minutes to complete).
3. Any participant reporting a personal or family history of adverse reactions to anesthetics will not be enrolled. If a participant reports any concerns or adverse reactions during the collection session, collection will immediately stop, and their participation discontinued.
4. If the participant is enrolled, they will be assigned a randomly generated identification number. All of their files and documents will be labelled with this number.
5. Each participant will also be randomly assigned to one of six possible task orders. Neither participants nor experimenters will be blinded to these conditions. This is documented in a hard-copy log.
6. Participants will be fit with an fNIRS cap to measure brain signals.
7. Then complete three computer generated tasks under four conditions (a, b and c will be randomized):
 - a. No sensory perturbation
 - b. Lollipop
 - c. Bite bar
 - d. Lidocaine – this condition will always be completed last.

8. The comparators to the lidocaine are no sensory perturbation, a candy lollipop and candy bite bar. All candy is obtained from the grocery store and are individually packaged. The lidocaine will be dispensed by a pharmacist and administered by the research team.
9. For the three computer generated tasks (randomly administered), accuracy and response time will be measured by the computer:
 - a. Task 1 (orthographic lexical decision): involves deciding whether a series of letters formulates a word or a nonword. Individuals will press the 'g' key if it is a word and the 'h' key if it is a nonword. Stimuli are single, monosyllabic, 4-7 letter length, words and nonwords.
 - b. Task 2 (phonological lexical decision): involves deciding whether a series of letters sounds out a word or a nonword. Individuals will press the 'g' key if it is a word and the 'h' key if it is a nonword. Stimuli are single, monosyllabic, 4-7 letter length, words and nonwords.
 - c. Task 3 (picture categorization): requires participants to make a judgement about whether a visually presented object is an animal or not. They will press 'g' if the object is an animal, and 'h' if it is not an animal.
10. Complete a short questionnaire rating and describing the numbness caused by the lidocaine (less than 5 minutes to complete).

Treatment

Each participant will swish 15 mL (one tablespoon) of the Viscous Lidodan 2% in their mouth for 60 seconds, then spit into a sink. This amount is the recommended manufacturer dosage. This will occur once during the one collection session. Viscous Lidodan 2% (i.e., Lidocaine Hydrochloride Oral Topical Solution 2% USP) is a topical anesthetic. The numbing effects of Viscous Lidodan 2% should take effect after five minutes and last around 30 minutes.

No other topical oral anesthetics are permitted to have been administered in the day before the trial. No details are required on any other medications.

Safety Assessment

Safety Assessment/Monitoring and Risk Mitigation. Each participant completes a pre-collection questionnaire where it asks all subjects to report any personal or family history of adverse reactions to anesthetics. This is a hard-copy questionnaire that is completed by the participant after the informed consent form, but before collection begins. It is reviewed together with the experimenter and participant before collection commences. Participants will be informed prior to beginning the experiment that they may withdraw at any time. They will be monitored throughout the experiment by research staff for signs of distress or adverse reactions (e.g., redness, itching or swelling of skin, hives, burning, stinging, or any other skin problems, swelling of the neck area, or any difficulty with breathing). The QI will be available via phone/pager during administration of Lidocaine in case of adverse event(s) for assessment/ triage/treatment/follow-up as clinically indicated.

If any reactions or adverse effects (i.e., redness, itching or swelling of skin, hives, burning, stinging, or any other skin problems, swelling of the neck area, or any difficulty with breathing)

are observed by the experimenters during collection, the QI will be called and the experimenter will escort the participant to the hospital emergency room connected to the Clinical Sciences Building. After the collection session is over, the participant will be instructed to report to their nearest emergency room if they experience any reactions or adverse effects. Participants will be informed that they should avoid eating and drinking and exposure to extreme hot or cold temperatures (e.g. food, drink) until complete sensation has returned. The numbness may also increase the risk of unintentional biting (e.g., cheek).

The lidocaine condition will always be lastly completed so its effects will not interfere with the other conditions. Each participant will be asked to complete a questionnaire after collection to localize and rank their numbness on a provided schematic. And adverse events reported by the participant will be recorded on this document and reported immediately to the qualified investigator. After the collection session is over, the participant will be instructed to report to their nearest emergency room if they experience any reactions or adverse effects. Topical anesthetics in the mouth may impair swallowing. The numbness may also increase the risk of unintentional biting (e.g., cheek). The qualified investigator, an otolaryngology head and neck surgeon, will follow-up with the subject as she deems appropriate. All serious unexpected adverse drug reactions (SUSARs) will be reported to Health Canada as mandated per C.05.014 (1) of the FDR.

Budget Considerations

Participants will be offered a small honorarium (\$20.00) for taking part in the study.

Experiment Location

6-104, Clinical Sciences Building, University of Alberta.

Statistical Analysis

Given the between groups nature of the sensorimotor perturbation (i.e., lidocaine vs. no lidocaine groups), we will first run a $2 \times 2 \times 4 \times 2$ ANOVA with group (lidocaine vs. no lidocaine), task (spell vs. sound), word type (exception words, regular words, pseudohomophones, nonwords), and time (pre-lidocaine vs. post-lidocaine), as the factors of interest. If the 4-way interaction is significant, a series of mixed ANOVAs will be run to test the effect of sensorimotor perturbation for each of the reading tasks. The independent variables will be time (pre-perturbation vs. post-perturbation), word type (exception, regular, pseudohomophone, nonword) and group. An ANOVA was also be run to test the effect of the sensorimotor perturbation for the control picture categorization task, with the independent variables including time (pre-perturbation vs. post-perturbation) and group. The dependent variable will include response time and accuracy. Bonferroni corrected t -tests were used to explore significant effects of the lidocaine on task performance. No interim analyses are planned. The data will be analyzed when thirty subjects have participated.

Data | Documents

The data will be kept confidential and no personally identifying information will be linked to the data. All data will be reported in aggregated form. The data and consent forms will be stored securely at the University of Alberta by the principal investigator. The investigators and institution will permit trial-related monitoring, audits, IRB/IEC review, and regulatory inspections, providing direct access to source data and documents.

All data and documents relating to the clinical trial will be stored for a minimum of twenty-five years after completion of the study.

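### Objective 2 compares dyslexic readers with an earlier study, while the 30 concurrent controls appear in no objective and no analysis

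*Combined protocol and SAP*

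**What the plan says.** **Objectives.** Under Purpose | Objectives, item 1 concerns perturbation effects "on reading performance (i.e., speed, accuracy) in adults with dyslexia". Item 2 is "To compare the findings with a previously completed study using a population of adults with typical (i.e., normal) reading abilities". Item 3, on how speech production contributes to reading, names no population.

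**Recruitment.** Under Participant | Subject Criteria: "Thirty adults (i.e., ≥ 18 years of age) of either sex or identified gender with diagnosed or self-reported dyslexia will be recruited", and then "Thirty participants (18+) without dyslexia will also be recruited as a control" group. Under Methodology, the two-session subset is given as "Twenty percent (i.e., 12) of recruited participants will complete" the protocol over two visits.

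**Exposure.** Under Treatment: "Each participant will swish 15 mL (one tablespoon) of the Viscous Lidodan 2% in their mouth". No exception is made for controls.

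**Analysis.** The Statistical Analysis section opens "Given the between groups nature of the sensorimotor perturbation (i.e., lidocaine vs. no lidocaine groups" and sets up an ANOVA "with group (lidocaine vs. no lidocaine), task (spell vs. sound), word type" and time (before or after lidocaine). It has no factor for dyslexia versus control, no factor for study, and no matching or adjustment for a comparison with the earlier study. Analysis is to begin once thirty subjects have taken part. No alpha, effect size or sample-size calculation is given.

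**The concern.** The dyslexia-versus-typical question has two possible comparators. The objective names the external one, and the design recruits an internal one that is assigned no comparison. If the text is followed literally, every dyslexic reader comes from this study and every typical reader in the stated comparison comes from another. Any feature of study conduct that changes how a perturbation acts on performance is then read as an effect of dyslexia.

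A group tested under the same protocol would remove that between-study component, and it is already planned. Thirty people would otherwise undergo the full session, including lidocaine, without a stated inferential purpose.

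**Working it through.** **1. Are the controls part of this trial?** The one figure that can be checked is the two-session subset, 12 participants at 20%.

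- Total 60 (30 + 30): 0.20 × 60 = 12, which matches.
- Total 30: 0.20 × 30 = 6, which does not.

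The controls are therefore counted among the recruited participants. The session steps and the Treatment section are also written for every participant.

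**2. Does any objective or analysis use them?** Objective 1 is confined to dyslexia, Objective 2 to the earlier study, and Objective 3 is silent. The between-person factor in the ANOVA is lidocaine versus no lidocaine. Under Treatment each participant takes lidocaine, so this factor has no second level. The thirty-subject trigger is half of the 60 recruited.

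**3. What bias survives?** Let the effect for one person be performance under a perturbation minus performance without it. A study difference that adds a constant to both conditions (setting, equipment, cap) drops out of the subtraction. A study difference that acts on one condition more than another does not. Methodology puts lidocaine last, after the other three conditions, so practice and fatigue are part of the lidocaine-minus-baseline effect. If the earlier study used another order or session length, that difference stays in the cross-study contrast. The protocol treats order and fatigue as open questions, since it sets aside 12 participants to examine them. In a within-trial contrast, a shift common to both reader groups cancels.

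**4. Illustrative size.** The documents do not give the earlier study's sample size, SD, condition order or session length. Assumptions:

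- a two-sample t-test at two-sided alpha 0.05;
- 30 dyslexic readers and n0 earlier readers;
- no true reader-group difference;
- a between-study shift b in the perturbation effect, in SD units of that effect.

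The standard error is √(1/30 + 1/n0), the noncentrality is b divided by that, and the degrees of freedom are 28 + n0.

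| n0 | SE | b = 0.25: noncentrality, false-positive rate | b = 0.50: noncentrality, false-positive rate |
|---|---|---|---|
| 20 | 0.289 | 0.866, 13.6% | 1.732, 39.7% |
| 30 | 0.258 | 0.968, 15.9% | 1.936, 47.8% |
| 60 | 0.224 | 1.118, 19.8% | 2.236, 59.9% |

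**5. What the concurrent contrast can detect.** With 30 versus 30 and the same test, 80% power needs a standardised difference of about 0.74. The normal approximation gives (1.960 + 0.842) × √(2/30) = 0.72.

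**The case against.** **The controls are probably meant to be compared.** Calling them a control group suggests this, and nothing forbids it. That is fair as a reading of intent, and it is why one cannot infer that the sponsor plans to leave them out. But intent stated in neither the objectives nor the analysis needs the same correction.

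**A within-person design protects against between-study differences.** This stands for level shifts. A reader might infer that every difference in setting, stimuli or equipment carries over in full. The documents do not support that, because the endpoint is performance with and without perturbation. Only differences that alter the effect itself remain.

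**The shift could be estimated.** A reader might also infer that no analysis could separate study from dyslexia. That is true only if the concurrent controls are left out. Comparing them with the earlier typical readers would estimate the study shift, which is a further reason to use them.

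**No test against the earlier study is specified.** This is correct. Objective 2 may mean a descriptive comparison, so the percentages above are not error rates of the plan. The Background also describes the team's earlier work with the same three perturbations and the same kinds of task, which suggests similar procedures. It gives no order, session length or sample size, so comparability is neither shown nor refuted.

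**Conclusion.** The concern holds in a limited form. As written, the only stated dyslexia-versus-typical comparison is across studies, and the 30 concurrent controls have no assigned role in the objectives or the analysis. The resulting confounding is avoidable. It is restricted to study differences that modify the perturbation effect, such as condition order, practice or fatigue.

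Its size is unknown. The ranges of 14 to 20% and 40 to 60% rest on assumed shifts, an assumed alpha, an assumed earlier sample size and a test that the plan does not specify. They show sensitivity and do not estimate a bias. It would also be too strong to infer that concurrent controls make the comparison unbiased. Reading status is not randomised, so differences such as age or education between the groups would remain.

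**What to change.** 1. Reword Objective 2 to compare perturbation effects between adults with dyslexia and the concurrently recruited adults without dyslexia.
2. In Statistical Analysis, replace the lidocaine/no-lidocaine group factor with reader group (dyslexia versus control), and test reader group × condition. The present group factor and the Treatment section contradict each other on who takes lidocaine. The sponsor must reconcile them, and this model follows the exposure described under Treatment.
3. Change the analysis trigger from thirty subjects to all 60 participants.
4. Keep the earlier study as a descriptive comparison, and report its condition order, session length and sample size beside this trial's.

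The cost is wording and a modest change to the model, with no additional participants or sessions because the controls are already planned. Two limits should be stated in the plan: the groups are not randomised, and 30 versus 30 has 80% power only for a difference of about 0.74 SD.

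### Withdrawing and replacing participants who cannot perform the reading assessments makes loss of primary-endpoint data depend on the outcome, and retaining their partial data does not cure this

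*Combined protocol and SAP*

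**What the plan says.** Under Participant | Subject Criteria, the withdrawal paragraph states: "Participants will be immediately withdrawn (i.e., collection stopped) if they are unable to perform reading assessments". The same sentence gives two other triggers, a reported adverse reaction and a wish to stop. For anyone withdrawn, "their data will be retained for analysis, unless the participant requests the data be destroyed". The paragraph then adds: "Any withdrawn participants will be replaced with additional recruitment". It does not define *unable*, and it does not name the stage or the task to which the word applies.

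Under Methodology, "The primary endpoint is reading response time and accuracy for each word type with and without oral perturbation". The endpoint tasks are two-key decisions timed and scored by computer. The no-perturbation, lollipop and bite-bar conditions come in random order, and lidocaine is always last. On masking, step 5 says: "Neither participants nor experimenters will be blinded to these conditions".

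The study population is thirty adults "with diagnosed or self-reported dyslexia will be recruited to participate in a within subjects repeated measures design", and "Thirty participants (18+) without dyslexia will also be recruited as a control" group. The Statistical Analysis section plans ANOVAs with time (before versus after the perturbation) as a factor. It gives no rule for incomplete participants and defines no analysis set. Analysis follows once thirty subjects have taken part, without saying whether these must be completers.

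**The concern.** A trial that recruits people because reading is hard for them, and then measures their reading, should not let difficulty with the measured task decide who is measured. As written, the rule permits that. A participant who cannot manage a task, in any condition, has collection stopped and the place is filled by someone who can. The inability is itself information about the endpoint, yet it does not enter the endpoint.

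Two results are exposed. One is the level of reading performance in the dyslexia group, and with it the comparison with typical readers. The other is the effect of each perturbation within a person, which is the first objective. Loss linked to a bad response would push that contrast toward no effect or toward facilitation.

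**Working it through.** **1. When does the rule apply?** The protocol could mean the pre-enrolment tests ("Self-reported reading disorders will be confirmed/verified prior to enrollment via standardized reading measures") or the experimental tasks. Three features of the text favour the session:

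- The withdrawal sentence itself explains withdrawal as the stopping of collection.
- The sentence before it deals separately with people who fail the criteria at first contact, who are never scheduled.
- The two companion triggers both operate during the session.

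**2. What does a stopped participant lack?** Because lidocaine is always last, a stop in any earlier condition loses all lidocaine data. Because the other three conditions are in random order, an early stop can also lose the no-perturbation baseline. A participant stopped during lidocaine has completed the other three conditions and has part of the fourth.

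**3. Does retention help?** The time factor in the ANOVA needs both a pre- and a post-perturbation value. A standard repeated-measures ANOVA uses complete cases, so a participant with no lidocaine data would normally fall out of the lidocaine contrast although the data are kept. The plan names no method that would use them.

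**4. How large could the bias be?** The documents give no withdrawal rate, SD, effect size, alpha, power or sample-size calculation, so there is no stated figure to reproduce. The following is an illustration. Assumptions: normal distributions; a share p withdrawn for inability, all from one tail; replacement up to n = 30 completers; withdrawn participants absent from the contrast.

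*Group level.* If those stopped are the weakest readers, the mean shifts by k = φ(z)/(1 − p), with z the upper p point of the standard normal. The SD becomes √(1 − z·k − k²) of its true value. For p = 10%: z = 1.282, φ(z) = 0.1755, so k = 0.1755/0.90 = 0.195, and the SD ratio is √(1 − 0.250 − 0.038) = 0.84.

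*Within-person contrast.* Let r be the correlation between inability and a harmful perturbation effect. The bias is r·k, in SDs of the within-person effect. Multiplying by √30 = 5.477 expresses it in standard errors at n = 30, using the SD before selection.

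| Assumed p | Level shift (SD) | SD ratio | Contrast bias, r = 0 | r = 0.3 | r = 0.5 | r = 1 | r = 1, in SEs |
|---|---|---|---|---|---|---|---|
| 5% | 0.11 | 0.90 | 0 | 0.03 | 0.05 | 0.11 | 0.59 |
| 10% | 0.20 | 0.84 | 0 | 0.06 | 0.10 | 0.20 | 1.07 |
| 20% | 0.35 | 0.76 | 0 | 0.10 | 0.17 | 0.35 | 1.92 |

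Enrolment needed for 30 completers is 30/(1 − p), rounded up: 32, 34 and 38.

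The level shift requires only that those stopped are the weaker readers. The contrast is biased only if r is above 0.

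**The case against.** The strongest reply is that inability is not poor performance. On a two-key task a very weak reader can still press a key, and slow or chance-level responses are recorded as endpoint data. A reader might infer that the rule removes the poorest dyslexic readers and those most impaired by a perturbation. The documents do not say so: no accuracy or speed threshold triggers withdrawal, and data collected before the stop are kept. This stands, and it limits the claim to what the rule allows.

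Second, nothing in the documents shows that a perturbation makes anyone unable to do these tasks. The background reports that, in the team's earlier adult study, lollipop and lidocaine each speeded responses on one task and the bite bar had no effect. This too stands as evidence against a large r. It does not settle the matter, because the protocol itself says it is not known whether those effects hold in adults with reading disorders.

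Third, the masking statement follows the task-order assignment and does not say who judges inability. It would go too far to conclude that unmasked experimenters make that call. Equally, no written criterion governs it. That controls would rarely be stopped is a reasonable inference from how the groups are defined, but the documents do not state it.

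Fourth, the phrase may refer to the screening tests. In that case the rule would affect generalisability and would not select on the perturbation effect. This reading is possible but weaker (step 1), and the text should settle it.

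**Conclusion.** The concern holds in a limited form. The rule allows loss and replacement that depend on the primary outcome, and the retention sentence does not repair this under a complete-case ANOVA. Whether bias results, and how much, depends on how often *unable* is invoked and whether it is linked to reading level or to the perturbation effect. The documents give neither.

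At an assumed 10% withdrawn, the bias in the within-person contrast lies between 0 and about 0.20 SD, the latter being about 1.07 standard errors at n = 30. The upper end requires a complete link and is a worst case. The direction, where there is a link, is to hide harm or exaggerate facilitation. The shift in the dyslexia group's level could reach the same 0.20 SD without any link to the perturbation, if those stopped are its weakest readers and are absent from the analysis.

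**What to change.** - Leave the adverse-reaction and participant-request triggers exactly as they are.
- Apply performance-based exclusion and replacement only before the first condition. Use a short practice block to check that the participant can follow the instructions and operate the keys.
- After that, do not withdraw or replace for low accuracy or slow responses alone.
- If a participant cannot continue a task, record the condition and the reason and keep the participant in the analysis set. Score unanswered trials as errors for accuracy, and treat response time as censored at a time-out, which the protocol must define. This does not require any block to be completed.
- Define the analysis set, and say whether the thirty who trigger analysis are completers.
- Replace the complete-case ANOVA with a mixed model on all available trials. That model alone does not handle loss that depends on the unseen outcome, so add a sensitivity analysis that scores inability as the unfavourable outcome.

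The cost is a few sentences in the withdrawal criteria and the Statistical Analysis section, a short practice block, and slightly more analysis work. Some near-chance or incomplete blocks will enter the data and add variance.
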